Patient self-assessments: Patients are asked to complete the 1) Voice Handicap Index (VHI): a questionnaire that evaluates the degree of handicap experienced by the patient in relation to their voice use(41); 2) the GFI(42): a validated disease-specific impairment instrument conceived to assess symptoms related to glottal insufficiency; 3) the RSI(43), a validated self-administered questionnaire to assess symptoms related to LPR; and 4) the Communicative Participation Item Bank (CPIB) general short form(44). Patients are also asked to rate their perceived phonatory effort (PPE) on a direct magnitude estimation scale(45) following the speaking and voicing tasks recorded with the CSL.

Aerodynamic measures: The Phonatory Aerodynamic System (PAS) is used to measure 1) mean glottal airflow rate: estimated from sustained phonation of a vowel(36); 2) average subglottal air pressure (P_s): measured during the production of a voiceless plosive consonant (/p/) at normal pitch and loudness, an accepted indirect and non-invasive measurement method for P_s (46); and 3) laryngeal resistance: calculated by dividing subglottal pressure by mean glottal airflow.

Phonation duration (MPT): The maximum phonation duration of the vowel /a/ is measured via CSL.

Respiratory measures (respiratory measures will be recorded solely as part of the study).

Spirometry: Spirometry will be used to measure 1) forced vital capacity (FVC), 2) forced expiratory volume in one second (FEV1), and calculate the 3) FEV1/FVC ratio. The predicted values (%) of these three measures will also be reported. The patient will be asked to take a full inspiration, blow out the air forcefully and then exhale slowly to residual volume in the spirometer. The task is repeated at least three times, until the two best measurements differ by no more than 0.15.

Muscle pressure measures: 1) MIP: measured at functional residual capacity, is an indicator of inspiratory muscle strength. Patients will be instructed to exhale fully and then inhale with maximal effort with lips sealed to the pressure meter for at least 2 seconds. 2) MEP: measured at full lung capacity, is an indicator of expiratory muscle strength. Participants will be instructed to take a full breath and then exhale with maximal force with lips sealed to the pressure meter for at least 2 seconds.

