Firstly, the medical chart of the participant will be reviewed to obtain the following information: height and weight. This information will be used to perform the respiratory and muscle pressure assessments. The medical chart will also be used to track the speech therapy appointments, since research visits will take place on the same days. Spirometry assessments will take place at baseline and after the fourth intervention session. Muscle pressure testing and acoustic assessments will be conducted at baseline and before and after each intervention session.

Spirometry: Prior to the tasks, the participant will put on a nose clip and make sure that the lips are well sealed around the tube with no air is escaping. They will be asked to breathe normally, and then take a full inspiration and blow out with force during at least 6 seconds, in the spirometer. Those maneuvers will be repeated at least three times, to verify test reliability. No more than eight repetitions should be needed(47). The participant is seated to reduce risks of fall.

• Muscle pressure (maximum inspiratory pressure-MIP- and maximum expiratory pressure-MEP):

- o MIP: the participant is instructed to exhale slowly and completely, seal lips firmly around the mouthpiece, and then breathe in forcefully. The PI will note the largest negative pressure sustained for at least one second on the pressure gauge. The participant will rest for about one minute and then repeat the maneuver up to 4 additional times (with the goal of matching the highest 2 trials within 10 cmH₂O)(48).
- o MEP: the participant is instructed to inhale slowly and completely, seal lips firmly around the mouthpiece, and then breathe out forcefully. The PI will note the largest positive pressure sustained for at least one second on the pressure gauge. The participant will rest for about one minute and then repeat the maneuver up to 4 additional times (with the goal of matching the highest 2 trials within 10 cmH₂O) (48).

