- Acoustic assessment: The microphone is positioned at a 45° angle and at a standardized distance from the mouth of the participant. The participant is asked to sustain phonation on the vowels /a/ and /i/ at a comfortable loudness for 3-5 seconds and as low and as loud as possible, to glide to a high pitch and to a low pitch, and from a soft voice to a loud voice. They are asked to sustain the vowel /a/ for as long as possible. They are then asked to read the 6 CAPE-V sentences and to have a short natural conversation with the speech therapist. The participant is then asked to rate their perceived phonatory effort (PPE) on a scale.
- Self-Assessment questionnaire: the participant will be asked to fill out the Communicative
 Participation Item bank (CPIB) questionnaire, which consists of 10 questions on communication.

Participants will be stratified based on their muscle pressure measures: 1) within normal limits MIP and MEP; 2) preserved MIP and decreased MIP; 3) preserved MEP and decreased MIP; 4) decreased MIP and MEP. This stratification is crucial to the study design because it will ensure an equal repartition of the

different respiratory profiles and deficits across treatment groups. Participants that don't meet stratification requirements will be excluded from the study.

Participants will be blocked-randomized into three groups (allocation ratio 1:1:1): IMST, EMST and VFE (see description of the interventions below).

Experimental Interventions (Procedures to be performed solely as part of this research study):

Participants in all groups will attend four sessions with a study team member. Intervention sessions will last approximately 30-45 minutes each. Each session will include pre- and post-treatment muscle pressure and acoustic measurements.

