
Sample Size Justification

We considered maximum phonation time (MPT) as the primary outcome measure for sample size calculation. This measure was chosen because 1) low MPT is a hallmark of patients with presbyphonia, and 2) MPT is directly affected by both the laryngeal and respiratory systems. To estimate the expected effect size between VFE and the I+IVFE and E+VFE groups, we considered MPT values from groups of an

elderly population with different glottal closure and spirometry profiles (49). Considering that a combined intervention (inspiratory or expiratory training combined with voice therapy) would address both laryngeal and respiratory deficits, and that a voice therapy-only intervention would directly address only the laryngeal deficits, we compared MPT between the no-deficit group (complete glottal closure and normal spirometry) and the respiratory-deficit group (complete glottal closure and altered spirometry)(49). Based on these values and the pooled standard deviations, the expected difference between our control and experimental groups would represent a large effect size. As for the withinsubjects effect, a study by Nam et al.(50) found a 33% increase in MPT following a respiratory training intervention program in young adult singers. This corresponds to a very large within-subjects effect size with values of d exceeding 1.2. For Aim 2, we will assess improvement in 2 ways: function (a MPT increase of 4 seconds, which has been associated with a positive perceived effect following voice therapy in older adults(51)) and patient perception of function (a Glottal Function Index (GFI) score decrease of 4 points). An increase of 4 seconds in MPT and a decrease of 4 points on the GFI instrument both correspond to medium-large effect sizes considering the reported standard deviations of these measures in older subjects and in patients with glottal insufficiency (5.1 and 4.5, respectively) (42, 52). Based on the reported studies, the expected effect size for within-subjects and between-subjects differences was set at d=0.90. To have an 80% power to detect an effect size of d=0.90 with an alpha of 0.1 (since this is a pilot study), 15 participants are needed in each group. To account for loss to follow-up (estimated 10% dropouts rate), up to 16 participants will be recruited for each group, 48 patients total.

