17.0 Sharing of Results with Subjects

During the course of the experimental sessions, the study team member will discuss the evolution of the respiratory outcomes with the participant. At the conclusion of the study, a study team member will offer to send an email to interested participants, with the findings from the study.

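### MPT, MIP, MEP and spirometry appear to be elicited and read by staff who know the arm, and respiratory progress is discussed before final testing; this may bias between-arm contrasts and is cheap to reduce

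*Combined protocol and SAP*

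**What the plan says.** Section 10.0 (Overview) restricts blinding to outcomes that need subjective judgement: videostroboscopy ratings and perceptual voice ratings, scored by speech-language pathologists who do not know the group. It describes no blinding for MPT, MIP, MEP or spirometry.

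The same section has every participant attend four sessions with a study team member, with muscle pressure and acoustic measures before and after each one. For MIP, "The PI will note the largest negative pressure sustained for at least one second on the pressure gauge"; MEP is read in the same way. Under Data Collection, the study team member records the spirometry, pressure and voice data. The team member also adjusts the training load each week from MIP or MEP (section 10.0) and brings the arm-specific trainer to the first session (section 18.0).

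For MPT, section 4.0 states: "The maximum phonation duration of the vowel /a/ is measured via CSL". Section 10.0 places a maximal sustained /a/ in the research acoustic assessment, but section 4.0 says that voice measures come from standard-of-care assessments.

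Section 17.0 provides that, during the experimental sessions, "the study team member will discuss the evolution of the respiratory outcomes with the participant". Table 1 puts therapy session 4 and the final assessment on the same visit.

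**The concern.** These outcomes are elicited as well as read. How long someone phonates, or how hard they pull against a gauge, depends on instruction, encouragement and the number of tries. If the person running the test knows the arm, any of these can differ by arm without intent. A value read live from a gauge also leaves room for judgement.

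The outcomes are central to the trial. MPT is the outcome on which it is sized. MIP, MEP and spirometry are the respiratory outcomes of Hypothesis 1 under Specific Aim 1. A gain of at least 4 s in MPT is one of the two markers of meaningful improvement in Aim 2. Staff would naturally expect the trained arms to do better, so a bias, if present, would probably favour them. Section 16.0 intends the results to inform patient management.

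**Working it through.** **Do the assessors know the arm?** The documents do not say so outright; it follows from combining roles.
- One role, the study team member, runs the sessions, sets the load, brings the device and records the data. That role cannot be unaware of the arm.
- The PI reads the pressures. Whether the PI is also the session team member is not stated, and nothing describes keeping the PI unaware of the arm.
- Who elicits MPT depends on whether section 4.0 or section 10.0 governs. Neither describes a blinded assessor.

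**How much discretion is there?**
- MIP and MEP: a common instruction, one attempt plus up to 4 more, the largest value sustained for one second, and a goal of the best two within 10 cmH₂O.
- Spirometry: at least three manoeuvres, with no more than eight expected.
- MPT: no number of attempts, scoring rule or encouragement text is given. The sizing outcome is the least standardised.

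**Whom does the feedback reach?** Section 17.0 speaks of the participant without naming an arm, and all groups attend sessions with pressure testing. The natural reading is that all arms receive it. It covers respiratory outcomes, and MPT is listed among the voice measures. Feedback therefore bears on MIP, MEP and spirometry. For MPT the route is elicitation and reading by staff who know the arm.

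**The plan's own figure.** Section 12.0 states: "To have an 80% power to detect an effect size of d=0.90 with an alpha of 0.1 (since this is a pilot study", then "15 participants are needed in each group". With two-sided alpha (sidedness is not stated) and the normal approximation:

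n = 2(z₀.₉₅ + z₀.₈₀)²/d² = 2(1.645 + 0.842)²/0.90² = 15.27 per group.

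Power at n = 15 is 0.794 by the normal approximation and 0.776 by the noncentral t. The stated 15 is thus reproduced closely. One-sided alpha of 0.10 would give 12, so two-sided is the matching reading.

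**What an assumed bias would do.** The documents give no size for a bias, so the values below are assumptions. Inputs: MPT SD 5.1 s (section 12.0), n = 15 per arm, two-sided alpha 0.10, no true effect, and one unadjusted comparison of a trained arm with control. The planned effect is 0.90 × 5.1 = 4.59 s. For a differential of b seconds, the standardised shift is b/5.1 and the noncentrality is (b/5.1)·√(15/2) on 28 degrees of freedom. For b = 1: 1/5.1 = 0.196; 0.196 × 2.739 = 0.537; 1/4.59 = 22%.

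| Assumed differential (s) | In SD | Share of 4.59 s | Rejection probability |
|---|---|---|---|
| 0 | 0 | 0% | 0.100 |
| 0.5 | 0.098 | 11% | 0.112 |
| 1 | 0.196 | 22% | 0.146 |
| 1.5 | 0.294 | 33% | 0.203 |
| 2 | 0.392 | 44% | 0.279 |

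The 5.1 s is reported for MPT in older subjects, not for change in MPT. If the analysed quantity varies less, a given bias in seconds weighs more; if it varies more, less. No comparable figure can be given for MIP, MEP or spirometry, because the documents state no SD for them.

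**What each remedy can reach.** Blinded timing protects the reading of MPT, but a phonation lengthened by encouragement is still longer when timed blind. It does nothing for MIP and MEP, for which no recording is described. A common script and attempt rule act on elicitation for all four measures. Deferred discussion acts on the respiratory measures only.

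**The case against.** The strongest reply is that no differential mechanism is shown. The feedback is not restricted by arm, and feedback common to all arms does not bias a between-arm contrast unless its content or effect differs. It does not cover MPT at all. Baseline testing precedes randomisation, so only later tests are exposed. The pressure and spirometry manoeuvres already have repeat and agreement rules. Participants cannot be blinded to a device, and unblinded assessment is common in a single-site pilot.

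Much of this stands. A reader might infer from section 17.0 that only the trained arms are told how they progress, or that this feedback inflates MPT; the text supports neither. A reader might also take 1 s or 2 s as an estimate of the bias, which it is not.

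Two parts do not answer the point. The existing rules for pressures and spirometry leave encouragement unscripted, and MPT has no such rule. Equal wording of the feedback provision does not make its effect equal: in a trained arm it reports on the capacity being trained and used to set the load, whereas in the control arm it does not. That makes a differential effect plausible, not demonstrated.

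A fair objection to the remedy is that weekly load resets still reveal progress to the trained arms. Deferring discussion therefore withholds information from controls that trained participants can partly infer. This limits what deferral achieves and should be acknowledged.

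**Conclusion.** The point holds as a risk of bias that the plan could reduce cheaply. Blinding is described only for stroboscopy and perceptual ratings. The effort-dependent outcomes, including the one that sizes the trial, appear to be taken by staff who know the arm, and respiratory results are discussed before the final tests. This may bias between-arm contrasts through encouragement, number of attempts or reading.

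The size cannot be derived from the documents. Under the assumptions shown, a 1 s differential in MPT would raise the false-positive rate from 10% to about 15%, and 2 s to about 28%. It would be too strong to conclude that final effort is biased, that the plan declares its assessors unblinded, or that blinded timing would remove a coaching effect. The conclusion rests on an inference from staff roles and on the natural reading that feedback reaches all arms.

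**What to change.** 1. Put the maximal /a/ token in the de-identified audio files. Have the blinded raters already planned, or a team member unaware of arm and time point, time MPT from them. For the two-level pre/post analysis this means 48 × 2 = 96 recordings.
2. Use one written instruction and encouragement text in all arms for MPT, MIP, MEP and spirometry. For MPT, also fix the number of attempts and state how the score is taken from them.
3. Amend section 17.0 so that individual respiratory results are not discussed until the final assessment is complete, and acknowledge that load resets will still reveal some progress to the trained arms. Load setting is not affected.
4. Reconcile section 4.0 (voice measures from standard-of-care assessments) with section 10.0 (maximal /a/ in the research assessment), and state who elicits and who reads each of the four measures and whether they know the arm.

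Cost: a script, and a small extra rating task that the raters' instructions and per-package payment must cover, since section 10.0 now assigns them only the CAPE-V and VALI forms. Participants also lose some motivational feedback; the weekly calls and compliance journal remain as adherence support. No new assessor is needed, and no sample-size input changes: 15 evaluable per group, and "up to 16 participants will be recruited for each group, 48 patients total".
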